3.32 Exclusion Criteria

- Those with bowel perforation
- Those taking chemotherapy or radiation treatment with absolute neutrophil count of < 1000 cells/mm3
- Those with colostomy or ileostomy or colonic strictures
- Those with subtotal colectomy or planning to have a colectomy
- Those with significant ileus

3.4 Stool donor selection and testing

Five universal stool donors registered with the Edmonton FMT program will provide the starting material, which is raw stool for patients recruited in Edmonton. These donors do not work in healthcare fields, and are known personally to the investigators. They are instructed not to provide a stool collection if they have any symptoms suggestive of an infection as per donor collection SOP and checklist in Appendix B.

They are rescreened every 2 months. The other sites included in the study have established stool donors in their facility and will provide their own FMT using identical protocol for donor screening and FMT manufacturing.

3.41 Donor stool collection and processing

Each donor will provide a fresh stool specimen, weighing approximately 100g, as per donor stool collection SOP (Appendix B). The stool specimen is stored at 4-8°C after collection and brought into the lab within 12 hours of collection. Donor stools should have the appearance of type 2-5 on the Bristol Stool Scale, and be free of blood, mucus or urine contamination. No pooling of stools will occur. Once received by the lab, it will be processed as per protocol for enema. Each donation of 100 g of stool will produce approximately 360 cc of fecal slurry, which will be stored frozen at -80°C as per our manufacturing protocol.

See Appendix A for donor screening SOP, Appendix C for donor questionnaire and Appendix D for donor consent.

3.5 Intervention and follow up

Patients who fulfill inclusion and exclusion criteria will be screened. Once consent has been obtained, metronidazole and vancomycin will be discontinued and 2L of Golytely will be administered the night prior to FMT. Each participant will undergo a large volume enema of 720cc delivered FMT on day 1, consisting of 200g of donor stool followed by two more days of small volume FMT enema on day 2 (360 cc) and day 3 (180 cc). This constitutes as cycle 1. In the event that a colonoscopy is indicated to rule out other pathology, then the scheduled enema can be delivered at the time of colonoscopy. On day 1, the patient will also start a 7-10 day course of fidaxomicin, as long as no clinical deterioration or complication such as bowel perforation has occurred. Following the first cycle of FMT treatment and fidaxomicin, careful clinical monitoring including vitals, requirement for vasopressors (if applicable), abdominal pain and distension, stool frequency and inflammatory markers including white blood cell (WBC) and C reactive protein (CRP) will be performed daily (Figure 3.0). If the patient has improvement in clinical parameters and inflammatory markers, and has reached a plateau without further changes over 24-48 hours after the first cycle, a second cycle of enema delivery of FMT will be administered. The FMT and fidaxomicin combined cycles will continue until clinical resolution of diarrhea and/or return of inflammatory markers to baseline prior to CDI. At that point, a final FMT 180cc enema will be administered. The maximal number of cycles is 4. At any time when a patient's conditions worsens, the study team will refer patient for surgery.

Each patient will receive FMT from a single donor with multiple collections obtained over time.

Baseline characteristics including age, sex, duration and response to CDI therapy, medical history (including inflammatory bowel disease, irritable bowel syndrome, baseline bowel habit, bowel resection, chemotherapy or radiation, number of CDI in the previous 12 months) and medication use will be collected. Blood work including CBC, electrolytes, creatinine, ALT, ALP, albumin, CRP, INR, HIV, and viral hepatitis serology will be drawn at screening visit (Figure 4.0). In addition, baseline collection of blood, and stool samples will be collected and

biobanked. Repeat stool and blood samples will be collected after each cycle of treatment, and again at week 1, 2, 4 and 8 after the final FMT.

Clinical status as well as monitoring for adverse events will be assessed daily up to 2 weeks after the final FMT while a patient is hospitalized, then weekly to week 8 after the final FMT. Patients are instructed to call as soon as there is recurrence of persistent diarrhea, and an unscheduled visit will take place if needed. Given COVID-19 pandemic, study follow-up may be conducted by phone if participants are unable to or do not want to attend study visits or if the visit is deemed non-essential by the principal investigator (PI). Due to this some of these sample collections may not be possible.

3.6 Subject Withdraw or Termination

Subjects will be discontinued from the trial in the following situations:

- Withdrawal of consent. The subject is free to withdraw from the trial without prejudice to further medical care
- Need for urgent colectomy

3.7 Outcome Measures

3.71 Primary Outcome

CDI resolution, defined as < 3 unformed bowel movements/ 24 hrs or a return to baseline bowel habit, 2 weeks after the last FMT treatment

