3.72 Secondary Outcomes

a) Sustained CDI resolution, defined as a lack of CDI recurrence 8 weeks after the last FMT treatment

Clinical status and biological samples will be taken to ensure that CDI has not recurred at 8 weeks

b) Adverse events

All serious adverse events will be recorded up to and including week 8 after the final FMT. A serious adverse event is any event which results in any of the following:

- Death
- Colonic perforation
- Proven infections related to FMT
- Subsequent hospitalization due to CDI within study period

c) Proportion of patients requiring colectomy

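### Both efficacy endpoints are timed from an undefined, response-triggered last FMT, and no rule scores further CDI treatment after it as failure

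*Protocol*

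**What the plan says.** Protocol 3.71 gives the primary outcome as "CDI resolution, defined as < 3 unformed bowel movements/ 24 hrs or a return to baseline bowel habit, 2 weeks after the last FMT treatment". Protocol 3.72(a) gives the first secondary outcome as "Sustained CDI resolution, defined as a lack of CDI recurrence 8 weeks after the last FMT treatment".

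Protocol 3.5 settles when enemas are given:

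- **Further cycle.** The trigger is improvement followed by a stall: the patient "has reached a plateau without further changes over 24-48 hours after the first cycle, a second cycle of enema delivery of FMT will be administered".
- **Stopping cycles.** "The FMT and fidaxomicin combined cycles will continue until clinical resolution of diarrhea and/or return of inflammatory markers to baseline prior to CDI".
- **Closing enema.** "At that point, a final FMT 180cc enema will be administered".
- **Cap.** "The maximal number of cycles is 4".
- **Worsening.** "At any time when a patient's conditions worsens, the study team will refer patient for surgery".

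The later paragraphs of 3.5 time sampling and follow-up from the *final* FMT, whereas 3.71 and 3.72(a) use the *last* FMT. If diarrhoea recurs in follow-up, the patient calls and an unscheduled visit is arranged if needed. Protocol 3.6 lists only withdrawn consent and urgent colectomy as grounds for discontinuation. Protocol 4.0 names a per-protocol approach for the primary outcome and has no rule for patients treated again.

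**The concern.** Two features of the anchor combine.

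First, it is triggered by response. A patient who stops cycling because diarrhoea has resolved starts the 2-week clock when the stool criterion is already met or nearly met. A patient who stops because markers have normalised may start it with diarrhoea still present. A patient who reaches four cycles unresolved, or is referred for surgery, has a last FMT but no closing enema. The same label thus marks different clinical moments, at different distances from first treatment.

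Second, it is not pinned down. Nothing says that the last FMT means the scheduled closing enema, and nothing says what happens to a patient's score if CDI is treated again afterwards. The primary outcome is a stool criterion at a single time point, so a relapse that has been treated by then leaves no trace in it.

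At stake is the headline result of a single-arm study of 30 patients. No concurrent arm shares the same ambiguity, and two careful analysts could score the same patient in opposite ways.

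**Working it through.** The protocol states no target rate, and 3.2 bases N = 30 on patient volume, so there is no planned figure to reproduce. The check has three parts.

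**1. How far the time origin moves**

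Inputs from 3.5: enemas on days 1 to 3 of a cycle, fidaxomicin for 7 to 10 days, a plateau of 24 to 48 hours, at most 4 cycles. Assumptions: a cycle occupies 3 days (enemas only) to 10 days (full fidaxomicin course), the plateau lasts 1 to 2 days, and the closing enema comes one day after the last cycle. For k cycles:

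- shortest closing day = 3k + 1(k − 1) + 1
- longest closing day = 10k + 2(k − 1) + 1
- 2-week assessment = closing day + 14; 8-week assessment = closing day + 56

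| Cycles | Closing enema (day) | 2-week assessment (day) | 8-week assessment (day) |
|---|---|---|---|
| 1 | 4 to 11 | 18 to 25 | 60 to 67 |
| 2 | 8 to 23 | 22 to 37 | 64 to 79 |
| 3 | 12 to 35 | 26 to 49 | 68 to 91 |
| 4 | 16 to 47 | 30 to 61 | 72 to 103 |

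Slightly different assumptions shift the ends by a day. With no closing enema after cycle 1 the assessment is on day 3 + 14 = 17; with a closing enema on day 48 it is on day 48 + 14 = 62. The 2-week assessment therefore spans 61 − 18 = 43 days, about six weeks.

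**2. What the literal wording does after a relapse**

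Take a closing enema on day 4, so that the scheduled assessments are on days 18 and 60.

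| Course after the closing enema | Literal scoring | Scoring with the anchor fixed at day 4 |
|---|---|---|
| Relapse on day 11, FMT that day, stools settle | Last FMT is now day 11; assessed on day 11 + 14 = 25; resolved | Non-resolution |
| Relapse on day 11, CDI antibiotics, fewer than 3 unformed stools on day 18 | Last FMT still day 4; resolved | Non-resolution |
| Relapse at week 5 (day 4 + 35 = 39), FMT that day, no later recurrence | New 8-week point on day 39 + 56 = 95; sustained | Recurrence by day 60 |

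FMT after relapse could thus affect both endpoints. Antibiotics affect mainly the primary one, because a relapse treated with antibiotics is still a recurrence under 3.72(a).

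**3. Size per patient**

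One patient moved from failure to success changes the rate by 1/30 = 3.3 percentage points; three would change it by 3/30 = 10 points. The documents give no relapse or retreatment rate, so the number of such patients is unknown.

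**The case against.** A reader might infer that the protocol lets FMT be given again after relapse, and so erases failures by design. The text does not support that. A further cycle follows improvement and a plateau, worsening leads to surgical referral, and recurrence leads to a call and, if needed, a visit. The natural reading is that *last* and *final* both mean the closing enema. Against this, reopening treatment is not barred, relapse is not a ground for discontinuation under 3.6, and a patient who resolved after one cycle has not reached the cap. The gap is silence on scoring.

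A reader might also put the overstatement at 10 to 20 points, by supposing that 3 to 6 of 30 patients relapse and are successfully given FMT again. No such rate appears, and the supposition assumes the very retreatment that the protocol does not describe.

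Nor is the endpoint simply circular. The stopping rule can be met on markers alone, some patients never meet it, and a relapse still present at 2 weeks fails. Repeat cycles before the closing enema are the strategy under test and are not failures. Assessing a strategy at its end is legitimate.

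It would also go too far to say that the rate cannot be compared with any other cohort. The published series described in the introduction likewise repeated FMT until a response criterion was met, and the historical comparison in the hypothesis concerns the number of FMTs and length of stay.

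Other records would catch some relapses: hospitalisation for CDI is a listed serious adverse event, and colectomy is a separate outcome. Neither feeds into the primary score.

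Finally, an analysis plan that is not shown may hold handling rules. But the anchor is part of the endpoint that 3.71 itself fixes, and as worded it admits opposite scores for one patient.

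**Conclusion.** The concern holds as a defect in the endpoint definition. Under 3.5 the anchor is tied to response, and its calendar position varies whenever courses differ in length. Under the assumed cycle lengths the 2-week assessment ranges from about day 17-18 to day 61-62. The term *last FMT* is left undefined, and later CDI treatment has no scoring consequence for the primary outcome.

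Any upward bias is conditional on patients being treated again after the closing enema. Its size cannot be computed from the documents beyond 3.3 points per reclassified patient. The conclusion does not rest on the protocol authorising FMT after relapse, and it does not treat planned repeat cycles as failures.

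**What to change.** Amend the scoring text in 3.71 and 3.72(a):

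- Define the last FMT as the scheduled closing enema or, where none is given, the last enema of the planned cycles.
- After that anchor, score any recurrence leading to further FMT or other CDI-directed therapy, or colectomy for CDI, as non-resolution if within 2 weeks and as not sustained if by week 8, whatever the later stool count. Completing the ongoing fidaxomicin course does not count as further therapy.
- Add a supplementary table of status at one fixed day from day 1, with the number of cycles received. The day should fall after the longest planned course (day 47-48 under the assumptions above) and before the shortest follow-up ends (day 3 + 56 = 59). Day 56 would serve, using the nearest recorded status. For the longest four-cycle course it is only 56 − 47 = 9 days after the closing enema, so the table supplements the primary outcome and does not replace it.

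The cost is wording in two sections and one table from the clinical status already collected under 3.5. Patient care is unchanged. The stated resolution rate may come out slightly lower.

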4.0 Proposed Analysis

The primary outcome, defined as CDI resolution at week 2, will be analyzed using the per protocol approach for all patients. Adverse events will be tabulated in each predetermined outcome.

To measure the direct medical costs, the utilization of different health care services, including pharmaceuticals, physician services, Emergency Department visits, inpatient hospitalizations, and Intensive Care Unit time will be summed for each individual patient. In order to attempt to attach a dollar value to the resource utilization, CIHI's Resource Intensity Weights (RIW) will be used. The RIW methodology derives estimated resource utilization compared to an 'average typical hospital stay', the cost of which has been calculated for the Edmonton Zone in each fiscal year from 2010/11 through 2014/15. RIW values are calculated based on the patient's Comprehensive Ambulatory Classification System (CACS) group, age and based on the patient's Case Mix Group (CMG) code, age, and comorbidity level.

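### The week-2 resolution outcome sets no condition on non-study CDI treatment, so a patient whom the regimen failed can be counted as a success or dropped, but is never clearly a failure

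*Protocol*

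**What the plan says.** Section 3.71, repeated in the synopsis, counts a patient as a success on this criterion: "CDI resolution, defined as < 3 unformed bowel movements/ 24 hrs or a return to baseline bowel habit". The time point is two weeks after the final FMT. The outcome depends on stool count or bowel habit alone.

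Other sections bear on a patient who receives other CDI treatment:

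- Section 3.5: "Once consent has been obtained, metronidazole and vancomycin will be discontinued". Nothing says how a later restart, or another CDI drug, affects the outcome.
- Section 3.5: patients who improve and then plateau get another cycle, and patients who worsen are referred for surgery. "The maximal number of cycles is 4".
- Section 3.6: "Subjects will be discontinued from the trial in the following situations". The two situations listed are withdrawal of consent and need for urgent colectomy.
- Section 4.0: the primary outcome "will be analyzed using the per protocol approach for all patients". The per-protocol set is not defined, and no concomitant drug is prohibited anywhere.

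Medication use is planned in two ways. It is a baseline item in section 3.5 ("number of CDI in the previous 12 months) and medication use will be collected"), and it is cost data in sections 3.73(a) and 4.0, drawn at least partly from an administrative database. The daily and weekly contacts in section 3.5 cover clinical status and adverse events.

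**The concern.** The resolution rate is the trial's main result, and there is no concurrent control against which to judge it. If a patient has not resolved on FMT plus fidaxomicin and then settles on a different CDI drug before day 14, the wording of 3.71 credits that result to the study regimen.

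The setting makes this plausible. The introduction reports earlier use of serial FMT with vancomycin, both at the sponsor's own centre and in a published series, so a drug other than fidaxomicin is an obvious option for a patient who is not resolving. The protocol neither describes nor forbids such use; it is silent on how the patient is then classified. Deciding that after the data are seen, in an open-label trial, would leave the main result open to a choice made with knowledge of outcomes.

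**Working it through.** **No plan figure to reproduce.** Section 3.2 bases N = 30 on patient volume. No target rate, success threshold, alpha or power is given.

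**Step 1: follow the patient through the text.** Take a patient who is unresolved after cycle 4 without worsening, or who relapses within 14 days of the last FMT, and who starts a non-study CDI drug.

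1. Section 3.5: not worse, so the surgical referral does not apply; for the first type of patient, no cycle remains.
2. Section 3.6: neither discontinuation reason applies, so the patient stays in.
3. Section 3.71: if the stool criterion is met at week 2, the patient is resolved by definition.
4. Section 4.0: on the words about all patients, the patient counts as a success. On the words about per protocol, the patient might be excluded, for example if restarting a drug stopped at consent is treated as a deviation.

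No section makes this patient a failure.

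**Step 2: compare the three ways of counting.** Let s be the patients resolved on the study regimen alone, and k those who meet the stool criterion after starting non-study CDI treatment. N = 30.

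- Counted as success: (s + k)/30
- Dropped: s/(30 − k)
- Counted as failure: s/30

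Excess over counting as failure:

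- Success: (s + k)/30 − s/30 = k/30, which is 1/30 = 3.3 points per patient.
- Dropped: s/(30 − k) − s/30 = s·k/[30(30 − k)]. Because s cannot exceed 30 − k, this is at most k/30.

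So 3.3 points per patient is the ceiling under either reading, and both excesses are upward.

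**Step 3: illustration.** s = 24 and the values of k are assumptions; the protocol gives neither.

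| k | Success | Dropped | Failure |
|---|---|---|---|
| 1 | 25/30 = 83.3% | 24/29 = 82.8% | 24/30 = 80.0% |
| 3 | 27/30 = 90.0% | 24/27 = 88.9% | 24/30 = 80.0% |
| 5 | 29/30 = 96.7% | 24/25 = 96.0% | 24/30 = 80.0% |

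Exact (Clopper-Pearson) 95% intervals for k = 3: 73.5 to 97.9% as success, 70.8 to 97.6% if dropped, 61.4 to 92.3% as failure.

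**The case against.** **The per-protocol analysis may remove these patients.** This stands in part. A reader might infer from 3.71 alone that every such patient certainly counts as resolved; section 4.0 is too ambiguous to support that. But dropping the patient also raises the rate (88.9% against 80.0% in the k = 3 example), so the problem remains.

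**The route is narrow.** Also partly right. Cycles run until resolution of diarrhoea and/or normalised inflammatory markers, and the final enema is given at that point, so for most completers the two-week clock starts after improvement. Most patients enter because metronidazole and vancomycin did not give an adequate response, and worsening leads to surgery. This limits how many patients are exposed, but does not classify those who are.

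**It belongs in the SAP.** Detailed handling rules may. The endpoint itself is fixed in the protocol, and an SAP cannot recover drug start dates that were not collected.

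**Stronger readings that the documents do not support.**

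- A reader might extend the point to week 8. That outcome is "Sustained CDI resolution, defined as a lack of CDI recurrence 8 weeks after the last FMT treatment". It is defined by recurrence and not by a stool count, so a patient treated for a recurrence has already failed it.
- A reader might say that medication is recorded only at baseline. Sections 3.73(a) and 4.0 also plan it as cost data. What is missing is a link to the efficacy outcome.
- A reader might want a fixed window without antimotility drugs or opioids before the week-2 count. The protocol never mentions these drugs for patients and gives no basis for a window. Such a rule would also leave the affected count neither success nor failure.

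**Conclusion.** The concern holds for the primary outcome. Read exactly, the protocol lets a patient whom the regimen failed count as resolved or, on another reading of section 4.0, leave the denominator. Both put the rate above what it would be with that patient as a failure.

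The only firm size is the ceiling of 3.3 points per patient at N = 30. The number of such patients is not given, so the total bias cannot be computed; the 10-point shift in the k = 3 example rests on assumed counts.

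This should be fixed, but it is not a fatal fault. The study is a pilot with no success threshold, so no formal decision turns on the rate. With 24/30 the exact interval already spans 92.3 − 61.4 = 30.9 points, so one patient matters little and several would matter.

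**What to change.** 1. **Section 3.71 (and synopsis):** add that a patient who starts any non-study CDI-directed treatment after the first study FMT and before the week-2 assessment is a non-responder, whatever the later stool count.
2. **Section 4.0:** state that these patients stay in the denominator, so that the per-protocol wording cannot remove them.
3. **Section 3.5 follow-up:** at the daily and weekly contacts already scheduled, record start dates of CDI-directed drugs and any antimotility or opioid use.
4. **Sensitivity analysis:** report the week-2 result by antimotility or opioid use at the time of the count.

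Section 3.72(a) needs no change on this account. The rule classifies outcomes only; it neither restricts nor recommends any treatment.

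Cost: one sentence in the outcome definition, one in the analysis section, and one added field at existing contacts. The reported rate may be slightly lower. The change should be made before outcome data accrue.

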Study Purpose	To determine the safety and efficacy of serial FMT and fidaxomicin in the treatment of severe or fulminant CDI
Study Design	Prospective, open label, multi-center study
Study Population	Patients with severe or fulminant CDI
Sample Size	30
Dosing	
Each cycle consists of:
 
 1. Serial FMT: 720 cc (1st treatment), 360 cc (2nd Rx), and 180 cc (3rd Rx) of fecal slurry 2. Fidaxomicin: 200 mg oral BID x7-10 days
Masking	None
Study Outcomes	
Primary outcomes
 
CDI resolution, defined as < 3 unformed bowel movements/ 24 hrs or a return to baseline bowel habit, 2 weeks after the last FMT treatment
 
Secondary outcomes
 
 1. Sustained CDI resolution, defined as a lack of CDI recurrence 8 weeks after the last FMT treatment 2. All serious adverse events up to and including week 8. A serious adverse event is any event which results in any of the following after the final FMT: 
 a. Death b. Colonic perforation c. Proven infection related to FMT d. Subsequent hospitalization due to CDI within study period 3. Need for colectomy

	
Exploratory outcomes
 
 1. All direct medical costs for CDI treatment 2. Changes in microbial composition, metabolomics and host immune response after treatment
Inclusion Criteria	
 1. Age > 18 years with severe¹ or fulminant² CDI, without an adequate response to metronidazole IV 500 mg q8H and vancomycin 500 mg PO q6h for at least 2 days or after a single Fecal Microbiota Transplant (FMT). An adequate response is defined as a decrease in stool frequency or inflammatory markers (WBC or C reactive protein) by at least 10% over 48 hours 2. Those with ability to provide informed consent or an alternative decision maker providing consent 
¹- Severe CDI defined as WBC > 15,000 cells/mm³ or serum creatinine level >1.5mg/dL or 1.5x premorbid level ²- Fulminant CDI defined as having any of the following attributable to CDI: Hypotension or shock, ileus, megacolon. An abdominal CT scan should be strongly considered to rule out perforation

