Fecal microbiota transplantation (FMT), which restores intestinal dysbiosis, is highly efficacious in treating mild to moderate recurrent CDI. There is also emerging evidence that FMT may be effective in severe or fulminant CDI, a situation where the only alternative is colectomy (8). FMT can be administered by difference routes, including enema, colonoscopy and oral capsules (9). However, Health Canada does not allow oral capsule to be administered outside the context of a clinical trial. Although few studies have described the efficacy of FMT in severe and fulminant CDI, it appeared efficacious and safe. For example, our group has successfully treated 6 patients with fulminant CDI with serial FMT plus vancomycin over the past year (Figure 2.0). These patients had avoided colectomy as a result. In addition, Fischer and colleagues demonstrated 17/19 (91%) clinical cure rate in these critically ill patients using combined serial FMT and vancomycin (10). In this protocol, Fischer described using colonoscopy-delivered FMT to treat fulminant CDI after failing at least 5 days of combined metronidazole and vancomycin. At the time of colonoscopy to deliver FMT, if pseudomembranes were noted, vancomycin was restarted for at least 5 days before the second colonoscopic FMT was administered. If pseudomembranes persisted, vancomycin was again given for 5 more days

before the third FMT was administered, and this cycle of FMT and vancomycin continued until pseudomembranes resolved. However, there are questions and uncertainties with this approach. First, vancomycin is not a narrow spectrum antibiotic, and it seems counterintuitive to give FMT and vancomycin at the same time. Second, the presence of pseudomembranes cannot be used for daily clinical monitoring, as it requires an invasive test. Furthermore, it remains unknown how many FMT each patient requires, what the most convenient or safest way to administer the FMT is, what the best strategies for monitoring is, or what the optimal frequency of FMT is. The success of Fischer's protocol thus also highlights the gaps in knowledge in mechanisms of action for FMT in severe or fulminant CDI.

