3.31 Inclusion Criteria

- Age > 18 years with severe¹ or fulminant² CDI, without an adequate response to metronidazole IV 500 mg q8H and vancomycin 500 mg PO q6h for at least 2 days or after Fecal Microbiota Transplant (FMT). An adequate response is defined as a decrease in stool frequency or inflammatory markers (WBC or C reactive protein) by 10% over 48 hours
- Those with ability to provide informed consent or an alternative decision maker providing consent

¹- Severe CDI defined as WBC > 15,000 cells/mm3 or serum creatinine level >1.5mg/dL or 1.5x premorbid level

²- Fulminant CDI defined as having any of the following attributable to CDI: Hypotension or shock, ileus, megacolon (4). An abdominal CT scan should be strongly considered to rule out perforation

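### The per-protocol primary analysis can drop colectomies and deaths before the 2-week assessment, because nothing in the protocol counts them as non-resolution

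*Protocol*

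**What the plan says.** - **Outcome.** Section 3.71 has resolution "defined as < 3 unformed bowel movements/ 24 hrs or a return to baseline bowel habit", 2 weeks after the last FMT. The synopsis agrees: "CDI resolution, defined as < 3 unformed bowel movements/ 24 hrs", with the same alternative and time point. Neither mentions survival, an intact colon or any other sign of disease.
- **Entry.** Section 3.31 admits severe CDI on white cell count or creatinine, and fulminant CDI on hypotension or shock, ileus or megacolon. It sets no minimum stool count. Section 3.32 excludes significant ileus.
- **Course.** Section 3.5 continues cycles "until clinical resolution of diarrhea and/or return of inflammatory markers to baseline prior to CDI", up to a maximum of four. Daily monitoring covers vital signs and "requirement for vasopressors (if applicable), abdominal pain and distension, stool frequency and inflammatory markers". If a patient worsens, "the study team will refer patient for surgery".
- **Discontinuation.** Section 3.6 gives two reasons for leaving the trial: withdrawal of consent and need for urgent colectomy.
- **Analysis.** Section 4.0 analyses the primary outcome per protocol and, in the same phrase, for all patients. It does not define the per-protocol set.
- **Where failures appear.** Section 3.72 lists death among the serious adverse events and colectomy as a separate proportion. Both are secondary outcomes.
- **What counted as success before.** Of six pilot patients, section 1.0 says: "These patients had avoided colectomy as a result".

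**The concern.** This is a single-arm study, so the resolution rate at 2 weeks is the efficacy result. The patients for whom treatment most clearly fails are those who go to colectomy or die. The protocol takes the first group out of the trial and has no outcome rule for either. If they are then left out of a per-protocol analysis, the rate describes only patients who got through the treatment period. Section 1.0 presents avoided colectomy as the success of the pilot, yet here a colectomy need not count against the primary result.

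A smaller worry concerns the outcome itself. A patient can qualify on shock, ileus or megacolon, but the definition looks only at stool. Few stools can reflect recovery, or a bowel that is not moving.

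**Working it through.** **Step 1: follow a failing patient through the text.**
1. The patient worsens and is referred for surgery (3.5).
2. If urgent colectomy is needed, the patient is discontinued from the trial, not only from treatment (3.6).
3. At 2 weeks after the last FMT the stool criterion cannot sensibly be applied after colectomy, and 3.71 gives no substitute.
4. Section 4.0 can then be read in two ways. If per protocol governs, the patient leaves the denominator. If all patients governs, the patient stays in but has no defined outcome. Neither reading makes the patient a stated failure.

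Death is not a listed reason for discontinuation. A patient who dies before the assessment nevertheless has no assessable stool outcome and meets the same gap.

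**Step 2: effect on the rate.** The planned size is 30 (synopsis and 3.2), based on patient volume, so there is no power calculation to reproduce. Let x be the number resolved among 30 treated patients and d the failures dropped:

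- true rate = x/30
- reported rate = x/(30 − d)
- ratio = 30/(30 − d), which is 1.034, 1.071 and 1.111 for d = 1, 2 and 3

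The ratio is never below 1, so dropping failures can only raise the rate.

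**Step 3: illustration.** The protocol gives no expected failure count. The one figure to borrow is the cited series of serial FMT with vancomycin: "17/19 (91%) clinical cure rate in these critically ill patients". (17/19 is 89.5%, not the printed 91%.) Two of 19 failed, and 30 × 2/19 = 3.2, taken as 3 failures, so x = 27. A lower rate of 21/30 is added as a second assumption.

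| d dropped | x = 27 (true 90.0%) | x = 21 (true 70.0%) |
|---|---|---|
| 0 | 27/30 = 90.0% | 21/30 = 70.0% |
| 1 | 27/29 = 93.1% | 21/29 = 72.4% |
| 2 | 27/28 = 96.4% | 21/28 = 75.0% |
| 3 | 27/27 = 100% | 21/27 = 77.8% |
| 9 | not possible | 21/21 = 100% |

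The exact (Clopper-Pearson) 95% interval is 73.5 to 97.9% for 27/30 and 87.2 to 100% for 27/27. The largest possible overstatement is the whole failure rate: 10 points in the first column and 30 in the second. It is reached only if every failure is dropped.

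**Step 4: the stool-only definition.** Each patient scored as resolved while fulminant disease persists adds 1/30 = 3.3 points. For this to happen, the patient must have few stools together with one of these at 2 weeks after the last FMT: megacolon, shock, or ileus that was mild at entry or arose on study. Section 3.32 removes significant ileus at entry, and 3.5 monitors daily and refers worsening patients for surgery. The case is possible on the wording but should be rare. Ileus as a qualifying feature in 3.31 and significant ileus as an exclusion in 3.32 also need to be reconciled.

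**The case against.** **The analysis set belongs in the SAP, and 4.0 does say all patients.** Definitions of analysis sets and the handling of such events are commonly left to an SAP, which is not shown here. That would answer a complaint about missing detail. But the protocol itself names per protocol as the primary approach, and an SAP that counted every colectomy as a failure would depart from 4.0 on that reading. The ambiguity is real, so the point is that failures *can* drop out. A reader might infer that the plan excludes deaths and colectomies outright, but no section says so. Referral for surgery in 3.5 is also not the same as need for urgent colectomy in 3.6, and only the latter ends participation.

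**Death and colectomy are reported anyway.** They are, in 3.72, so a careful reader would see them. The primary rate is not corrected by that.

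**The stool definition is a reasonable design choice.** Largely accepted. A reader might infer that low output from fulminant disease would regularly be scored as resolved, or that patients could pass through four cycles without any response. The documents support neither. Section 3.32 excludes significant ileus, and under 3.5 a second cycle follows improvement and then a plateau.

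**The repair is uneven.** Severe CDI qualifies on white cell count or creatinine, and the proposed clause tests neither. It also adds an unmasked judgement of what is attributable to CDI. Both remarks stand, which is why the clause is the lesser part of the fix and the stool-only result should still be reported.

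**Conclusion.** The point holds for the analysis. Sections 3.6, 3.71 and 4.0 together allow colectomies and deaths before the 2-week assessment to leave the primary denominator, and nothing in the protocol counts them as non-resolution. The direction is known: dropping failures raises the rate by the factor 30/(30 − d). The size is not known. The step from 90.0% to 93.1% or 100% rests on a failure count borrowed from a 19-patient series with a different regimen, and on an assumed number dropped. A reader might take 10 points as the expected bias, but it is only the upper end of one illustration; the true effect could be zero or, with more failures, larger.

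The stool-only definition is a minor point, worth 3.3 points per affected patient, and such patients should be few.

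This should be fixed before analysis. Confidence is medium, because 4.0 can be read either way.

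**What to change.** **Section 4.0.** Make the primary analysis include every patient who received at least one FMT. Count death or colectomy up to 2 weeks after the last FMT as non-resolved, including patients discontinued for colectomy. Count patients with no 2-week assessment, such as consent withdrawals, as non-resolved too, with a sensitivity analysis for that choice. Report the per-protocol result as supportive, with its set defined.

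**Section 3.71 and the synopsis.** Add to the stool criterion that the patient is alive, has not had a colectomy, and has no documented ongoing CDI-attributable shock, ileus or megacolon. Judge this from the clinical status assessments already scheduled in 3.5. Report the stool-only version as supportive.

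**Cost.** A few sentences in 4.0 and one clause in 3.71 and the synopsis. No new visit, test or imaging is needed: clinical status is already assessed daily to 2 weeks in hospital and otherwise weekly, and death and colectomy are already outcomes in 3.72. The reported rate may be slightly lower. For patients followed by phone, as 3.5 allows, absence of the fulminant features is inferred, not examined.
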